Chronic temporomandibular joint (TMJ) disorders (TMD) are the main cause of facial pain, and the second cause of musculoskeletal pain after low-back pain. The cause of TMD is unknown and therapy is usually empirical. Systematic reviews have shown that more research is needed to elucidate the benefits of occlusal adjustment for TMD. The risk factors for chronic unilateral TMD include dental (occlusal) premature contacts and habitual chewing on the affected side; therefore, a new occlusal therapy is proposed to restore physiological jaw closure and chewing function.

Aims

The primary endpoint will be the average change in pain score from baseline to the six-month assessments.

Efficacy will be demonstrated by superior pain relief with the active treatment compared with the placebo.

Methods

Study design

A phase 3, randomized, single (extensible to up three) centre, 6-month parallel-group, patient- and observer-blinded, placebo-controlled clinical trial to assess the efficacy of occlusal adjustment on recovery of physiological jaw closure and chewing function in patients with TMD.

Study population

Inclusion criteria: TMD patients, aged 18-65 years with full dentates and normo-occlusion suffering significant pain (pain scores ≥ 4 and ≤ 9 ; method: visual analogue/numerical rating scale (VAS/NRS); 0 = no pain, 10 = worst imaginable pain). Main exclusion criterion is the requirement of excessive enamel removal to equilibrate the dental articulation (occlusion).

Intervention

Active therapy will consist of the elimination of premature tooth contacts and the reduction of the steeper lateral anterior guidance. *Placebo* therapy will be conducted in a manner identical to the active adjustment, but no enamel will be removed.

Outcomes

Main outcome: self-reported pain intensity on the affected side measured by the VAS and/or NRS scale.

Secondary outcomes: maximum comfortable mouth opening (using a Boley gauge), chewing function (observed on the habitual chewing side) and quality of life using self-administered tests. Time frame: baseline and both 3- and 6-months follow-up.

Sample size estimation

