Based on data from a previous study, we assume a standard deviation of 2.4 for this variable. We will test the null hypothesis of no treatment effect at the two-sided 0.05 level. With a fixed sample size design, a total sample size of 88 subjects (extended to 110 for drop-outs) with complete follow-up would provide power of 0.8 to detect changes in pain score of 1.5 units between the active and placebo treatment groups.

Interim analysis plan and stopping rules

The Data and Safety Monitoring Board will be responsible for activating early stopping. The study will employ an interim analysis plan with a single interim analysis after 70% of participants have completed the six-month follow-up visit. Using the Lan-DeMets version of the O'Brien-Fleming stopping rule, the critical value for statistical significance at the interim analysis (under both intention-to-treat and *per-protocol* sets) will be +2.438, corresponding to a nominal two-sided P value of 0.0146.

Statistical analysis plan

For analysis of baseline characteristics, qualitative variables will be expressed as frequencies and percentages (25th -75th percentiles) and continuous variables as means (standard deviation). Fisher's exact or McNemar tests will be used to compare the distributions of binary variables; Student t test or measurements repeated analysis of variance will be used to compare normal variables, and the Wilcoxon or Mann-Whitney U test for non-normally distributed continuous variables.

All analyses will be conducted by two independent statisticians according to the intention-to-treat approach (the primary outcome was also analyzed as per protocol).

The objective of this analysis is to adjust regression models that explain the outcomes of interest as a function of time and group. Based on the properties of the analyzed variables, the model fit of the analyses based on the linear mixed-effects model or the beta mean regression model with mixed effects, using the Akaike Information Criterion or the Bayes Information Criterion. Plots of residuals were used to check that the model assumptions were met and to assess goodness of fit. Statistical significance level was set at 0.05. All the analyses were conducted using the software R (R Development Core Team), including the "lme4" and the "gamlss" packages or IBM SPSS24.

Sponsor

University of Santiago de Compostela, [name]

Funder

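### The SAP's only modelling rule leaves pain between a linear and a beta mixed model, so the primary six-month test is not fixed in advance

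*Combined protocol and SAP*

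**What the plan says.** All places are in the combined protocol and SAP.

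- **Aims:** "The primary endpoint will be the average change in pain score from baseline to the six-month assessments".
- **Study population:** pain is scored on a bounded scale, "0 = no pain, 10 = worst imaginable pain".
- **Sample size estimation:** 88 patients with complete follow-up (110 with drop-outs), SD 2.4, two-sided 0.05, power 0.8 to "detect changes in pain score of 1.5 units between the active and placebo treatment groups".
- **Interim analysis plan and stopping rules:** "a single interim analysis after 70% of participants have completed the six-month follow-up visit", with a critical value of 2.438.
- **Statistical analysis plan:** the objective is to "adjust regression models that explain the outcomes of interest as a function of time and group". The next sentence opens "Based on the properties of the analyzed variables" and offers a "linear mixed-effects model or the beta mean regression model with mixed effects, using the Akaike Information Criterion or the Bayes Information Criterion". As it stands, that sentence has no main verb.

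The SAP also gives the intention-to-treat approach, a per-protocol analysis of the primary outcome, the 0.05 level, and two independent statisticians. No section assigns a model family to pain, names a group-by-visit term or six-month contrast, or says which coefficient tests the null hypothesis.

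**The concern.** The endpoint and the sample size are stated in points on a 0 to 10 scale, so the intended comparison can be inferred: the group difference in mean change at six months. The modelling text does not commit to it. A bounded pain score fits either family, so the rule does not settle pain without looking at the data.

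If AIC or BIC is applied to pain, three things follow:

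1. The primary test is selected from the outcome data. The plan does not say that the selection is made blind to group.
2. The selection can come out differently at 70% and at the end, although one boundary scheme is meant to cover one test statistic.
3. If beta regression wins, its usual logit link gives a log-odds effect. That is not the points difference named as the endpoint and used for sizing. Scores of exactly 0 or 10 lie outside the ordinary beta model, and no rule is given for them. AIC values for the two families are comparable only if both are fitted to the same rescaled response, which is also not stated.

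**Working it through.** **The plan's sample size.** Inputs from the sample size section: difference 1.5, SD 2.4, two-sided 0.05, power 0.8. Equal allocation is assumed.

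- Normal approximation: 41 per arm, 82 in total.
- Exact t test: 42 per arm, 84 in total.
- The t-test number divided by a rank-test efficiency of 0.955: 42/0.955 = 43.98, so 44 per arm, 88 in total.
- Drop-out: 88/(1 − 0.20) = 110.

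The 88 is matched only through a rank-test allowance that the plan does not mention.

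**Power of the six-month change contrast.** The plan does not say whether 2.4 is the SD of the change or of a single visit. Taken as the SD of the change, with 44 per arm, the noncentrality is 1.5/(2.4 × √(2/44)) = 2.93 on 86 df, and power is 0.826. Taken as the SD at each visit, the variance of the change is 2 × 2.4² × (1 − ρ). Power by the normal approximation is then 0.70, 0.83 and 0.97 for correlations ρ of 0.3, 0.5 and 0.7.

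**What linear versus beta does.** This was simulated with 5,000 trials in each of 12 null and 12 effect scenarios. The Monte Carlo SE at 0.05 is √(0.05 × 0.95/5000) = 0.003. All of the following are assumptions, not plan figures:

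- 88 completers, complete data, SD of change 2.4;
- baseline mean 6.5, clipped to 4 to 9; follow-up clipped to 0 to 10;
- placebo six-month mean 3, 4 or 5; integer or one-decimal scores;
- baseline-to-follow-up correlation 0.5 with 0.7 between follow-ups, or 0.3 with 0.5;
- effect 1.5 points at 3 and 6 months before clipping (1.2 to 1.4 after).

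Both models had group, visit, group-by-visit and a random intercept. They were fitted by maximum likelihood to the same scores, rescaled to 0 to 1 and squeezed by (y(N − 1) + 0.5)/N. The test was on the six-month interaction.

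| Quantity | Range over scenarios |
|---|---|
| Type I error, fixed linear | 0.045 to 0.059 |
| Type I error, AIC-selected | 0.050 to 0.068 |
| Type I error, beta always | 0.059 to 0.072 |
| AIC picks beta, null trials | 11 to 100% |
| Pick at 62 completers differs from pick at 88 | 0 to 19% |
| Families disagree on significance, null | 3 to 5% |
| Families disagree on significance, true effect | 6 to 11% |
| Power, fixed linear (random intercept) | 0.77 to 0.83 |
| Power, AIC-selected | 0.78 to 0.85 |

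The interim count is 0.70 × 88 = 61.6, taken as 62. Part of the beta excess comes from the Wald test itself: when the beta mixed model is true, its type I error was 0.058 (3,000 trials).

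**AIC against BIC.** Each model has 8 parameters: 6 fixed effects and 2 variance or precision terms. With equal counts the two penalties cancel in the comparison, so AIC and BIC always choose the same model here.

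**Scale.** For a placebo mean m, a 1.5-point reduction corresponds to an odds ratio of [(m − 1.5)/(11.5 − m)]/[m/(10 − m)]. For m = 3 this is (1.5/8.5)/(3/7) = 0.41. For m = 4, 5, 6 and 7 it is 0.50, 0.54, 0.55 and 0.52. The same points effect therefore has no single value on the beta scale. In the simulation 4 to 28% of six-month scores were exactly 0 or 10, a share that depends on the clipping.

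**The case against.** The strongest reply is that the opening words of the modelling sentence can be read as choosing the family by type of variable, in which case no data-driven choice is made for pain. That is a fair reading of an incomplete sentence, and the point is conditional because of it. It does not close the gap, since a 0 to 10 score qualifies for either family.

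A second reply is that an information criterion is itself a prespecified rule and that two independent statisticians run the analyses. Both facts count. They rule out picking by P value, so the 0.072 to 0.087 type I error obtained by taking the smaller of the two P values is not what the plan allows. Duplicate analysis, however, does not say which test is primary.

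A third reply is that 6 to 11% disagreement is not remarkable. In 8,000 simulated trials a t test and a Mann-Whitney test on the same change scores disagreed in about 5%, and change-score and baseline-adjusted analyses in 2 to 7%. This stands: the disagreement is only modestly above that between standard tests, and it is a reason to fix the test rather than a sign of large bias.

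Stronger readings that a reader might infer, and that the documents do not support:

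- *The test is an additive group term that averages in the baseline visit.* The SAP names time and group but does not say the model is additive, and the Aims section fixes the endpoint as change to six months. Power lost under that reading is not expected harm.
- *AIC or BIC is a further free choice.* With equal parameter counts it is not.
- *The model was chosen after the data were seen.* Some SAP sentences are in the past tense, but that does not show when the choice was made.

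**Conclusion.** The point holds in conditional form. The plan does not assign pain a model family or a six-month contrast, and its one stated rule, if applied to pain, selects the primary test from the outcome data and may give an effect on a scale that does not estimate the stated endpoint. A serious loss of type I error control is not shown: the ranges for AIC selection and for the fixed linear model overlap, and part of the gap is the beta Wald test. The practical consequences are the 6 to 11% of trials with a true effect in which the reported significance depends on the family, the possible change of family between looks (0 to 19%), and the mismatch with the 1.5-point target.

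These figures rest on assumed means, correlations, clipping and boundary handling, on complete data although 110 recruited for 88 implies 20% loss, and on 2.4 being the SD of change. The change belongs among those that should be made; confidence in the size is medium.

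**What to change.** For pain, replace the AIC/BIC choice with one primary analysis used at both the interim and the final look: a linear mixed model on the 0 to 10 score at baseline, 3 and 6 months, with group, visit and group-by-visit, testing the group difference in change from baseline to six months. State the random-effects or covariance structure in advance. A baseline-adjusted version is equally acceptable if fixed in advance: its power is 0.83 to 0.87 against 0.83, assuming a baseline SD of 1.44 and correlations of 0.3 to 0.7.

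Keep beta regression as a sensitivity analysis, with a stated rule for 0 and 10 (for example zero/one inflation) and its effect back-transformed to points. If the sentence meant choice by variable type, assign pain to the linear model explicitly and say which outcomes get the beta model. Date the change relative to unblinding; the documents do not show whether unblinding has already taken place.

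The cost is SAP wording, with no change in sample size. The downside is giving up a possibly better-fitting primary model. In the simulation that was worth at most about 0.04 to 0.05 of power, part of it bought by the beta test's higher type I error.
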